4.4.5 History of Smoking [year]

Calculated as follows.

- 1) Currently smoking = (Day of Procedure – Since when smoking (For information up to year/month, use yyyy-mm-01 with 01 complemented to the day)/ 365.25
- 2) Past smoking
Number of years stated in “Smoking History”

4.4.6 Hemodialysis treatment history [year]

Calculated as follows.

Hemodialysis treatment history [year] = (Day of Procedure – Starting date of Hemodialysis/ 365.25

4.4.7 Number of years currently in use of vascular access

Calculated as follows.

Number of years currently in use of vascular access = (Day of Procedure – Day of creation of vascular access used currently)

4.4.8 Number of days until reintervention

Calculated as follows.

Number of days until reintervention = Date of (First) reintervention - Day of Procedure

※ “Number of days until reintervention for the first treated lesion” is for the first reintervention for which the answer to “Purpose of reintervention” is the “Patency of the initial implanted device”.

- ※ “Number of days until reintervention for vascular access circuit (Other than first treated lesion) is for the first reintervention for which the answer to “Purpose of reintervention” is the “Patency of vascular access circuit (excluding a site of initial implantation of the device)”.

5. Items related to Statistical Processing

5.1 Significance Level, Confidence Coefficient

The significant level of the test is 5% two-sided, unless otherwise specified. When interval estimation is performed, it is two-sided unless otherwise specified, and the confidence coefficient is 95%.

5.2 Details of Statistical method

5.2.1 Summary Statistics

In this statistical analysis plan, summary statistics mean the number of patients, mean, standard deviation, minimum, median and maximum values.

5.2.2

1000 1000 1000

ANSWER

[View Details](#)

— 1 —

1

ANSWER

For more information, contact the Office of the Vice President for Research and Economic Development at [contact] or [contact].

[REDACTED]

Displayed Digit of Calculated value

1 Displayed Digit of Summary Statistics, etc.

[figure not shown]
Round off the last 2 digits of displayed

[figure not shown]
5.3.2 Displayed Digit for Percentage and the Confidence interval

Round off to the third decimal place and displayed to the second decimal place.

[figure not shown]
5.3.3 Displayed digit of p value

[figure not shown]
Round off to the fourth decimal place and displayed up to the third decimal place. In addition, if the value is less than 0.001, $p < 0.001$ is shown.

[figure not shown]

8.1 [REDACTED]
8.1 Incidence rates of adverse events related to the device and the procedure at the time of treatment and up to 30 days post-treatment

Title of Table : 8.1 Incidence rates of adverse events related to the device and the procedure at the time of treatment and up to 30 days post-treatment

Analysis Patients with completed study form

object :

Contents of Analysis : For adverse events observed up to 30 days after the procedure, the following analysis is performed for each onset date of events: the date of procedure and from 1 to 30 days after the procedure.

- Calculate the overall number of sites, target patients, patients with adverse events, number of cases with adverse events, and incidence of adverse events
- Calculate the number of patients with adverse events, incidence of adverse events, and the number of cases with adverse events for each SOC/PT by the time of occurrence
- The denominator of incidence rate is the number of patients for the study.
- If a patient has multiple occurrences of the same SOC/PT at the same time, it is counted as one case in the case-counting. The number of cases is not summarized, but all are counted.
- If a patient has multiple occurrences of the same SOC/PT at different time points, count one case at each time . The number of cases is not summarized, but counted at each time point.
- The denominator of incidence rate is the number of patients for the study. Refer to “4.4.2.2 Adoption Range of number of patients for study of adverse events/ device deficiency” for the calculation method for the number of patients for the study.

8.2 [REDACTED]

Contents of Analysis :

- The following analysis is performed for each category of “4.4.2.1 Adoption Range for Adverse Event / Device Deficiency”
- Calculate the overall number of sites, target patients, patients with adverse events, number of cases with adverse events, and incidence of adverse events
- Calculate the number of patients with adverse events, incidence of adverse events, and the number of cases with adverse events for each SOC/PT by the time of occurrence
- If a patient has multiple occurrences of the same SOC/PT at the same time, it is counted as one case in the case-counting. The number of cases is not summarized, but all are counted.
- If a patient has multiple occurrences of the same SOC/PT at different time points, count one case at each time . The number of cases is not summarized, but counted at each time point.
- The denominator of incidence rate is the number of patients for the study. Refer to “4.4.2.2 Adoption Range of number of cases for study of adverse events/ device deficiency” for the calculation method for the number of patients for the study.
- The same analysis is performed for patients with On-Label use
- Analysis of the device and procedure-related adverse events and serious adverse events is conducted in a similar layout. Analysis is also conducted for adverse events, and adverse events and serious adverse events related to the device and the procedure similarly in the categories of under 65 years old/ 65 years old and older and under 75 years old/75 years old and older.

[figure not shown]
8.3 List of occurrences of device deficiency and infectious disease in post-marketing study, etc. (Appendix Form 3-3)

Title of Table : 8.3 List of occurrences of device deficiency and infectious disease in post-marketing study, etc. (Appendix Form 3-3)

[figure not shown]
Analysis object : Patients with completed study form

[figure not shown]
Contents of Analysis :

- The following analysis is performed for each category of “4.4.2.1 Adoption Range for Adverse Event / Device Deficiency”
- Calculate the overall numbers of sites, target patients, patients with device deficiency, and cases of device deficiency, as well as incidence of device deficiency
- Calculate the numbers of patients, incidence for each adverse device effect (or an infectious disease if it occurred) by the time of occurrence
- If a patient has multiple occurrences of the same device deficiency at the same time, it is counted as one case in the case-counting.
- If a patient has multiple occurrences of the same device deficiency at different time points, count one case at each time .
- If both known and unknown cases exist in the same event, they are counted as separate events, and the unknown event is presented first
- An unknown event is indicated by prefixing the event name with “*”
- The denominator of incidence rate is the number of patients for the study. Refer to “4.4.2.2 Adoption Range of number of patients for study of adverse events/ device deficiency” for the calculation method for the number of patients for the study.

9.4 List of Cases

Title of Table : 9.4 List of Cases

Analysis Enrolled patients

object :

Contents of Analysis : • Show the list of study items for each patient. The time period is specified in the study form as follows.

- 1 month
- 3 months
- 6 months
- 12 months
- 24 months

- Refer to the output plan for the study items and the details.

9.5 List of Mortality Cases

Title of Table : 9.5 List of Mortality cases

1

Analysis object : Enrolled patients

Contents of Analysis : • Show the cause of death, days to death, causal relationship, course of occurrence, details of treatment for each patient who “Died” as the outcome of an adverse event. In addition, the following items on the study form are shown.

- Cause of death: Name of adverse event
- Causal relationship: Causal relationship judgement
- Course of occurrence: Course of occurrence of adverse event
- Treatment: Treatment for adverse event

The day to death is defined as the number of days from the date of the procedure to the date of outcome of the adverse event (Date of outcome of the adverse event – Date of procedure).

10. References

Nothing in particular

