#### **(1) Treatment**

- Patient information
  - Age, sex, height, weight, smoking history, family history of myocardial infarction, treatment history of ischemic heart disease, etc.
- Medical history
  - Myocardial infarction, transient ischemic attack, etc.
- Primary disease / Complication

- Primary disease : diabetic nephropathy, chronic glomerulonephritis, nephrosclerosis, polycystic kidney disease, chronic pyelonephritis, interstitial nephritis, rapidly progressive glomerulonephritis, nephritis associated with autoimmune diseases, etc.
- Complication : dyslipidemia, hypertension, diabetes mellitus, metabolic syndrome, heart failure, peripheral arterial disease, stroke, etc.
- Pre-procedure information
  - Echocardiography, electrocardiography, assessment of cardiac function, laboratory data (BNP, etc.), etc.
- Characteristics of lesion
  - Location of the lesion, palpation, auscultation, etc.
- Secondary lesion information in the vascular access circuit after the procedure
- Procedure information at the time of treatment
  - Procedure time, blood flow before and after the procedure, vein pressure, etc.
- Information on Viabahn
  - Item and Lot Number
- Other device information used during treatment

(2) Follow-up information

- Information on vascular access and Viabahn
- Information on dialysis treatment continuation
- Information on discontinuation

(3) Failure

- Name of failure, date of occurrence, etc.

(4) Adverse events

- Name of adverse event, date of onset, severity, causal relationship, etc.

(5) Re-treatment

- Information on vascular access and lesions
  - Blood flow and venous pressure before and after re-treatment, palpation,

---

 Lesions not treated with Viabahn at the treatment

 Refers to the blood flow through the entire shunt.

 Refers to static venous pressure (sVP) or dynamic venous pressure (dVP). The venous pressure should be measured by the same method before and after the initial placement and before and after re-treatment of each patient.

auscultation, etc.

- Information on re-treatment
  - Performed treatment, clinical indications, etc.
- Other device information used during re-treatment

(6) Concomitant drugs (antiplatelet drugs, etc.)

- Drug Name
- Date of first administration
- Date of completion of administration

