**Table3 Adverse events and failures in this surveillance**

Adverse events	Any unfavorable or unintended sign (including abnormal laboratory changes), symptom, or illness associated with the use of a medical device. Unless worsening of severity or increasing of incidence during the surveillance, the primary disease of the patient is not considered an adverse event.
Device Defect	Defects such as damage, malfunction, etc. that are widely unfavorable. Regardless of whether they are due to design, marketing, distribution, or use. Medical device failures include the following: 

(1) Specification issues

(2) Defective product

(3) Malfunction or damage

(4) Insufficient description of package inserts, etc.

(5) Device-related adverse events

Serious adverse events are defined as any of the following adverse events.

- (1) Death
- (2) Disability
- (3) Cases that may lead to death
- (4) Cases that may lead to disability
- (5) Requires hospitalization or prolongs an existing hospitalization
- (6) Serious according to the cases listed in (1)~(5) above
- (7) Any congenital disease or anomaly in the offspring of treated patient.

The term "hospitalization" in (5) does not include hospitalization (scheduled surgery, examination, etc.) intended only to carry out the scheduled therapy or examination before the surveillance during the surveillance period (however, any newly occurring during that hospitalization should be handled as an adverse event).

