**Table5 Evaluation of the outcome for adverse events**

Outcomes	Criteria
Recovery	In the case of disappearance / recovery of the adverse event and the adverse event related to laboratory values, normalization or recovery to values before placement level of the surveillance device
Remission	Reduced degree of the adverse event or with a tendency to improve
Not recovered	Little change in the extent of the adverse event or those with exacerbation
Death	Mortalities associated with the adverse event
Unknown	Undertaken the follow-up of the adverse event but have not been able to follow the outcome

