3.2 Safety endpoint

3.2.1 Adverse Event/ Device deficiency

Term	Definition
Adverse Event	Any undesirable or unintended signs (including abnormal laboratory results), symptoms, or diseases occurring related to the use of a medical device. A patient's primary disease is not considered an adverse event unless it aggravates in severity or increase in frequency during the study.
Device deficiency	A condition that is not good in a broad scope, such as fracture, malfunction, regardless of whether it is caused by design, manufacture, distribution, or use. Device deficiencies include: (1) Specification problem (2) Defective product (3) Malfunction/fracture (4) Insufficient description in the insert, etc. (5) Adverse events caused by the device
Serious Adverse Event	Serious adverse events are defined as any of the following among adverse events. (1) Death (2) Disability (3) May lead to death (4) May lead to disability (5) Requires hospitalization or prolonged hospitalization for treatment in a hospital or a clinic (6) Serious cases similar to those listed in (1) though (5) (7) Congenital disease or abnormality in future generations

Term	Definition
Unanticipated Device Deficiency/Adverse Event	Device deficiency and Adverse Event not described in the insert are classified as “Unanticipated Device deficiency/Adverse Event”.

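### The mortality list in SAP 9.5 takes deaths only from adverse-event outcomes, so a death that a site does not enter as an adverse event could be left out

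*SAP*

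**What the plan says.** SAP 9.5 sets the population of the mortality list as "Analysis object : Enrolled patients". Within that population it selects patients who died "as the outcome of an adverse event". The contents of the list come from the same record: "Cause of death: Name of adverse event", the causality judgement for that event, its course and treatment, and days to death computed as "Date of outcome of the adverse event – Date of procedure".

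The documents bear on what enters that record in four places:

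- **Definition.** Protocol Table 3 describes an adverse event as an unfavourable sign, symptom or illness "associated with the use of a medical device". SAP 3.2.1 has the equivalent: "symptoms, or diseases occurring related to the use of a medical device". Death is a seriousness criterion in both, but it classifies events that already count as adverse events.
- **Causality.** Protocol Table 4 and SAP 3.2.1.1 both include a category for adverse events unrelated to the device or the procedure.
- **Outcome.** Protocol Table 5 defines the outcome Death as "Mortalities associated with the adverse event".
- **Other data.** Protocol 8.1(2) collects "Information on discontinuation" as part of follow-up. SAP 3.3.1 refers to a field for the reason for discontinuation; the only reason that can be read there is an 'Other' option.

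**The concern.** A list of all deaths lets a reader check that no device-related death has been missed or misclassified. It can do that only if entry to the list does not depend on someone having first decided how to classify the death.

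Here entry depends on the site having opened an adverse-event record and closed it with a fatal outcome. The definition, taken literally, gives a site a reason not to open a record for a death it considers unrelated to the device. The causality table gives another site a reason to open one and mark it unrelated. If the first reading is followed, the judgement on causality is made by leaving the form blank. It is then neither recorded in the causality field nor visible to anyone reading list 9.5.

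Uneven reading is a realistic possibility. Protocol section 5 says the surveillance aims to include physicians who have not used the device before.

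**Working it through.** No alpha, power or rate enters this point, and the plan states no figure to reproduce. The check is to follow a death through the rules as written.

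**Step 1: what SAP 9.5 requires.** The patient must be enrolled and must have an adverse-event record whose outcome is death. No second condition is stated.

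**Step 2: apply the rule to the ways a death could be recorded.**

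| How the death is recorded | Appears in list 9.5? |
|---|---|
| Adverse event, fatal outcome, judged related | Yes |
| Adverse event, fatal outcome, judged unrelated | Yes, shown as unrelated |
| Adverse event meeting the seriousness criterion Death, but outcome entered as something else (e.g. unknown) | No |
| No adverse event; death noted only in discontinuation or follow-up information, if those fields record it | No |

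**Step 3: is the last row compatible with the documents?** The definitions in Protocol Table 3 and SAP 3.2.1 tie an adverse event to device use, so a site that reads them literally may make no entry for a death it considers unrelated. Listing death as a seriousness criterion does not prevent this, because the criteria apply only to events that already meet the definition. The second row is equally compatible, because the causality tables provide for unrelated events. The documents therefore allow two treatments of the same death, and only one of them reaches the list.

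**Step 4: is there a second place where the death could be recorded?** Protocol 8.1(2) collects discontinuation information. SAP 3.3.1 counts discontinuation as a patency event only when the reason is 'Other', which implies that further reasons exist. Whether death is one of them cannot be read, so this route is an inference.

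**Step 5: does anything reconcile the two?** No readable text in either document adds deaths from another field to list 9.5 or compares adverse-event outcomes with discontinuation data.

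**Step 6: size.** The number omitted is (deaths among enrolled patients) × (share with no adverse-event record of fatal outcome). The documents give neither factor, so no estimate follows from them.

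**The case against.** The strongest reply is that unrelated events are plainly expected in the adverse-event data, whatever the definition's wording. Both causality tables have an unrelated category. Protocol 9.2 separates device- and procedure-related events up to 30 days (endpoint 1) from adverse events in general (endpoint 2). SAP 8.2 analyses related events in addition to all adverse events. The definition itself admits worsening of the patient's primary disease. List 9.5 prints a causality item for each death, and Protocol Table 5 ties the fatal outcome to the adverse event, not to the device. All of this stands. A reader might infer that adverse events are restricted to device-associated ones, or that the list is filtered by the site's view of relatedness. The documents do not support either reading: an unrelated death entered as an adverse event would be listed. What remains is a conflict between the definition and the causality table.

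Second, a reader might infer that deaths are in fact recorded only as a reason for discontinuation and so are left out. The readable text does not name death as such a reason, and the relevant field names are blacked out. The omission is a possibility, not a documented fact.

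Third, safeguards may exist out of sight. SAP 9.4 lists study items for every enrolled patient, some tables are redacted, and SAP 4.1 refers to a data management plan that could hold a death query. This stands in part. Such a death might appear in list 9.4, but that is a general listing whose items are left to a separate output plan, and its readable text sets out no cause of death, causality or reconciliation. If the reconciliation is already specified elsewhere, one sentence in SAP 9.5 saying so would settle the matter.

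**Conclusion.** The point holds as a minor one. The selection rule in SAP 9.5 rests on a single source, and the definition feeding that source conflicts with the causality table. A death not entered as an adverse event with fatal outcome could therefore be missing from list 9.5. The conclusion concerns that list only and rests on the readable text; redacted tables or separate plans could already cover the gap.

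A reader might be tempted to put a count on it. Assuming yearly mortality of 5% to 15%, two-year mortality is 1 − (1 − 0.05)² = 9.8% to 1 − (1 − 0.15)² = 27.8%, or about 10 to 28 deaths per 100 patients. This does not give the number missing. The mortality is an assumption, and the share without a fatal adverse-event record could be anything from none to all, so the result runs from 0 to 28 per 100. The target of 100 in Protocol section 3 is also for indicated cases only, whereas list 9.5 covers all enrolled patients, including the other uses admitted by Protocol section 4. The point does not depend on a count, because one omitted death is enough to make the list incomplete.

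**What to change.** 1. In SAP 9.5, select every enrolled patient with a death in any collected field: adverse-event outcome, the seriousness criterion Death, and discontinuation or follow-up information if it records death.
2. For each death show the source field, the date, the cause and the causality judgement. Where there is no adverse-event record, take the date from the field that reports the death and leave missing items visibly blank.
3. Add a data-management check that queries any death without a matching adverse-event record.
4. Align the adverse-event definition in Protocol Table 3 and SAP 3.2.1 with the unrelated category in Protocol Table 4 and SAP 3.2.1.1, so that sites know an unrelated death is to be entered.

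The cost is a wider selection condition, one data-management check and a wording clarification. The selection uses fields already collected, so no new data item is needed.
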